Although anger and aggression are commonly observed in military veterans with PTSD, there are few interventions that have been developed and tested to treat anger and aggression in this population. Mindfulness may be one such treatment that would be particularly useful in decreasing anger and aggression as it could (1) more effectively target the PTSD-specific symptoms most strongly associated with aggression, (2) assist veterans with PTSD in achieving awareness and insight into their anger states, which is important for the regulation of anger and aggressive reactions, and (3) be easily implemented and would not require a large time commitment from individuals. Findings showing that MBSR is effective in reducing anger and aggressive behavior in veterans with PTSD would be important as it could be an additional treatment that could be offered to veterans with PTSD who are struggling with these problems. Such an intervention could help decrease anger and prevent the perpetration of aggression among veterans with PTSD, thus preventing the detrimental consequences that anger and aggression can have on the lives of veterans, their families, and society at large.

Research Plan:

Overview: The proposed project will examine whether Mindfulness Based Stress Reduction (MBSR) decreases anger and aggression in veterans with PTSD. This project also will examine two potential mechanisms of action of MBSR: physiological reactivity and emotion regulation. This project will examine the initial efficacy of MBSR in a pilot randomized controlled study with 60 veterans with PTSD experiencing problems with anger and aggression. Participants will attend a baseline laboratory session to assess initial levels of self-reported anger and aggression and will then be randomly assigned to participate in a group PTSD psychoeducational course (the Trauma Recovery Education Course (TREC)) or group MBSR. After completing TREC or MBSR, all participants will participate in a post-treatment laboratory session in which self-reported anger and aggression will be assessed. In addition, during the laboratory session, participants will complete an experimental portion where they will be exposed to trauma-related stimuli, followed by participation in an experimental paradigm designed to assess aggressive behavior. After completing the post-treatment session, all participants will attend a 3-month follow-up session to assess long-term gains in the management of anger and aggression.

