Participants:

[figure not shown]
Inclusion Criteria: We will enroll 60 veterans with PTSD. To be eligible for the study, participants must meet current DSM-V diagnostic criteria for PTSD (American Psychiatric Association, 2013). PTSD will be established by interview using the Clinician Administered Posttraumatic Stress Disorder Scale for the DSM-V (CAPS-5; Weathers et al., 2013a). Participants must also indicate current difficulties with anger and aggression as indicated by a score of 20 or higher on the trait anger scale of the State Trait Anger Expression Inventory-2 (STAXI-2, Spielberger, 1999), indicating moderate to severe anger problems. Veterans from all eras will be eligible to participate.

Exclusion Criteria: Participants with a current diagnosis of bipolar disorder, psychotic disorder, or current substance use disorder with severe symptoms. Participants also must not have a seizure disorder and must not be taking any medications that would affect cognition or behavior on the aggression task, including pain medication, benzodiazepines, or antipsychotics. Participants also must not have a positive drug (e.g., amphetamine, opiates, and cocaine) or alcohol urine screen at the post-treatment session (see below), as these substances could affect performance on the study tasks implemented at that session. Finally, participants must not currently be receiving concurrent individual therapy or group therapy focused on anger and aggression and must not currently be participating in the modified TREC group offered at the West Haven VA (WHVA).

Research Design and Methods

For an overview of the time line for study procedures, see Figure 2.

Figure 2. Timeline of Study Procedures

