Trauma Scripting Procedure. After completing the diagnostic interviews (CAPS-5/SCID-5-RV), eligible participants will participate in a trauma-script development procedure as part of a well-validated, script-driven trauma imagery task (Pitman et al., 1987). For this procedure, participants will be asked to identify their most traumatic experience. If they identify more than one event, they will be asked to choose the one that they consider the most distressing. They will first be asked to describe the experience in writing using a script preparation form and then will be asked to indicate which of several different subjective visceral and muscular reactions (e.g., heart beating slower/faster, feeling sweaty, stomach in knots, feeling warm, hands trembling, tension in arms, nausea) may have accompanied the experience. Participants’ written responses will then be reviewed and they will be asked to clarify or expand on the details if necessary. After the session, a script lasting approximately 60 seconds in duration will be composed that portrays the traumatic experience in the second person, present tense, and incorporates the different visceral or muscular reactions. The script will then be audio recorded for playback

during the experimental portion of the post-treatment session. A research assistant (who will be named later upon being hired) will read the narrative scripts to be audio-recorded.

During this baseline session, participants will also complete a battery of self-report questionnaires (see below for full details) to assess baseline levels of anger and aggression.

Randomization Procedures. After participants have completed the Baseline Screening and Evaluation Session they will be randomized to either the TREC group or the MBSR group. To decrease the amount of time participants have to wait before starting group treatment, randomization will be implemented at the group level. That is, after 6 participants are recruited, they will be randomly assigned using urn randomization procedures, to either the TREC group or the MBSR group.

Post-treatment Session: After all participants have completed their assigned interventions (TREC or MBSR) they will be scheduled for the post-treatment session to be held in the biological studies laboratory at the WHVA. At this session, all participants will complete a battery of self-report questionnaires to assess post-treatment levels of anger and aggression (see below).

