Secondary Aim 1, Hypothesis 1.2: Within the MBSR group, decreases in physiological reactivity and increases in emotion regulation will be associated with decreases in aggression on the TRT. Pearson product moment correlations will be calculated to examine the association between changes in HR, SC, and emotion regulation and the TRT responses (i.e., mean shock level across the TRT and total number of “20” shocks chosen on the TRT).

Sample Size and Power Considerations

Although the proposed sample size may not be sufficient in establishing statistical significance but rather a pattern of results that suggest promising effects across anger outcomes, it is important to emphasize that the fundamental purpose of the pilot trial is to provide information for the planning of a future large scale clinical trial examining the efficacy of MBSR in decreasing anger and aggression in veterans with PTSD and examining additional mechanisms of action (i.e., behavioral, cognitive, social, biological) that lead to behavior change. To that end, the pilot RCT data will be used in power calculations to calculate the sample size for a later full-scale RCT examining MBSR for anger and aggression for veterans with PTSD.

Effect sizes for determining the sample size for the larger RCT will be calculated based on differences between the baseline and post-treatment scores on the self-report measures of

anger and aggression (STAXI-2, BPAQ), as well as the difference scores between the physiological measures (i.e., HR and SC) and emotion regulation obtained during the experimental portion of the post-treatment session. Comparisons will be made using a two-sample t-test. Due to the possibility that estimation of effect sizes based on pilot studies may be inaccurate (Kraemer et al., 2006), we will implement procedures recommended for improved characterization of effect sizes derived from pilot studies (Thabane et al., 2010). These include close consultation with clinicians who have used the treatment (i.e., [name]), and accounting for the effect size uncertainty by constructing confidence intervals around the observed effect size.

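### The next trial is to be sized from effect sizes observed in about 30 patients per arm, with no rule for which outcome or which part of the confidence interval sets N

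*Combined protocol and SAP*

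**What the plan says.** All the relevant text is in the combined protocol and SAP.

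- **Size.** Participants (Inclusion Criteria): "We will enroll 60 veterans with PTSD". No alpha, power, expected effect, SD, ICC or dropout is given to support the figure.
- **Allocation.** Randomization Procedures: "after 6 participants are recruited, they will be randomly assigned using urn randomization procedures, to either the TREC group or the MBSR group". Randomisation is described as being at group level, so 60 patients make about ten groups.
- **Limited power.** Sample Size and Power Considerations concedes that this size may not establish significance but rather "a pattern of results that suggest promising effects across anger outcomes".
- **Purpose.** Same section: "the fundamental purpose of the pilot trial is to provide information for the planning of a future large scale clinical trial".
- **Use of the pilot effect.** Same section: "Effect sizes for determining the sample size for the larger RCT will be calculated based on differences between the baseline and post-treatment scores" on the STAXI-2 and BPAQ, together with difference scores for heart rate, skin conductance and emotion regulation. The arms are to be compared by a two-sample t-test.
- **Safeguards.** The same section acknowledges that pilot effect sizes may be inaccurate. It plans consultation with clinicians who have used the treatment, and "accounting for the effect size uncertainty by constructing confidence intervals around the observed effect size". It gives no confidence level and no rule for moving from the interval to a sample size. A clustering adjustment of the next trial's N follows.
- **Tests in this trial.** Data Analyses specifies intent-to-treat mixed models with therapy group as a random effect and Bonferroni adjustment.

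**The concern.** The task that the plan calls fundamental is to size the next trial, and the input it chooses is the one that a pilot of this size estimates worst. A required N varies with the inverse square of the standardised effect, so a modest error in that effect becomes a large error in N.

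Five measures are listed and none is named as the one that decides. An interval is promised, but the plan does not say whether its lower limit, its centre or some other value will be used, or what happens if it includes zero. Two analysts following the text faithfully could arrive at very different trials.

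At stake is a full-scale trial that is too small to detect a useful effect, or one far larger than necessary.

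**Working it through.** The plan contains no sample-size figure to reproduce beyond N = 60, so the check asks how well a pilot of this size could set the next N.

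**Inputs from the documents.** 60 patients; groups of 6; effect sizes from a two-sample comparison.

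**Assumptions not in the documents.** An even split (5 groups, 30 patients per arm; urn randomisation need not give exactly this). No dropout. True standardised effect d of 0.3, 0.5 or 0.8, in SDs of the score compared. ICC 0 to 0.10. Next trial at 80% power, two-sided 0.05. An N is computed only when the observed d is above zero.

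**Step 1: what the next trial needs.** N per arm = 2(1.96 + 0.8416)²/d² = 15.698/d². This gives 175 at d = 0.3, 63 at d = 0.5 and 25 at d = 0.8, before clustering. A correct clustering factor multiplies the needed and the planned N alike, so their ratio does not change.

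**Step 2: precision of the pilot effect.** SE(d) ≈ √[(2/30)(1 + 5 × ICC)] = 0.258 at ICC 0, 0.289 at 0.05 and 0.316 at 0.10. The 95% half-widths are 0.51, 0.57 and 0.62.

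**Step 3: one observed result, several trials.** Suppose the pilot shows d = 0.5 (ICC 0).

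- Point estimate: 63 per arm.
- 95% upper limit, 0.5 + 0.506 = 1.006: 15.698/1.012, so 16 per arm.
- 80% lower limit, 0.5 − 1.2816 × 0.258 = 0.169: about 550 per arm.
- 95% lower limit, 0.5 − 0.506 = −0.006: no finite N.

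The plan's text permits any of these.

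**Step 4: spread of the plug-in N by hand (true d = 0.5, ICC 0).** Observed d ~ N(0.5, 0.258).

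- P(d ≤ 0) = Φ(−1.94) = 0.026, leaving 0.974.
- 90th percentile of N: the lower-tail point of d is 0.026 + 0.1 × 0.974 = 0.124, so d = 0.201 and N = 387.
- 10th percentile of N: d = 0.835 and N = 23.
- Within 25% of 63 (N from 48 to 78): observed d between about 0.449 and 0.578, probability 0.1975/0.974 = 20%.
- True power below 50% (N of 30 or fewer): observed d above 0.723, probability 0.1935/0.974 = 20%.
- More than double the need (N above 126): observed d below 0.353, probability (0.2845 − 0.026)/0.974, about 26.5%.

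The same normal approximation, by simulation:

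| True d | ICC | Needed | N, 10th-90th | N, quartiles | Within 25% | Power < 50% | N > 2 × need |
|---|---|---|---|---|---|---|---|
| 0.3 | 0 | 175 | 38-1826 | 63-413 | 13.6% | 35.1% | 27.8% |
| 0.3 | 0.05 | 175 | 33-1912 | 56-400 | 12.6% | 38.5% | 27.0% |
| 0.5 | 0 | 63 | 23-387 | 34-135 | 20.2% | 19.9% | 26.5% |
| 0.5 | 0.05 | 63 | 21-459 | 32-142 | 18.5% | 22.9% | 27.4% |
| 0.8 | 0 | 25 | 13-72 | 17-41 | 33.2% | 9.2% | 17.7% |
| 0.8 | 0.05 | 25 | 12-83 | 16-43 | 30.0% | 11.8% | 20.0% |

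**Step 5: simulation with groups and an estimated SD.** Simulating 5 groups of 6 per arm and estimating the SD from the pilot widens the spread slightly. At true d = 0.5 and ICC 0 to 0.10, the 10th percentile of N is about 18-21 and the 90th is 380-514. N is within 25% of the need in 17-20% of pilots, gives true power below 50% in 22-28%, and is more than double the need in 26-28%.

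**Step 6: does the interval help?** With SE = √(2/30 + d²/120), the 95% interval includes zero in 74-79% of pilots at true d = 0.3, about 51% at d = 0.5 and 14-18% at d = 0.8. In those pilots its lower limit gives no finite N. An interval that allowed for therapy groups would be wider.

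**The case against.** **The plan knows the problem.** It raises the inaccuracy of pilot effect sizes itself, plans intervals and clinical consultation, and adjusts for clustering. This stands as credit. It does not close the gap: consultation is not tied to any figure, the interval has no stated use, and the clustering step rescales an N that already carries the error.

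**The results depend on an assumed effect.** They do. At d = 0.8 the interval usually excludes zero and the spread is much narrower, although N is still within 25% of the need in only about a third of pilots.

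**The harm is deferred, and the alternative is partly a matter of method.** No estimate or test in this trial changes, and the documents contain no minimum important difference. Both points are fair, and they limit the severity. But planning the next trial is the stated purpose here.

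**Three stronger readings are tempting, and the documents do not support them.**

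- A reader might infer that the pilot's conclusion rests on a loose rule about a favourable pattern. The words stand in a clause conceding limited power, no decision hangs on them, and Data Analyses sets Bonferroni-adjusted tests.
- A reader might add that such a rule would be met at least half the time under no effect. No rule exists, so no rate can be assigned. Under no effect, both self-report outcomes would favour MBSR in 30-37% of pilots, and all five measures in 10-24%, for the outcome correlations tried.
- A reader might infer that the next trial would more often than not be underpowered. Counting pilots with observed d at or below zero as leading to no trial, about 50% of all pilots give an N with less than 80% power. Any roughly unbiased estimate would do the same. The fault is imprecision in both directions.

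**Conclusion.** The concern holds for sizing the next trial and should be acted on. The plan makes observed pilot effects the basis of that N without naming the deciding outcome or a use for the interval. Under the assumptions listed, with a true d of 0.5, about four pilots in five would give an N more than 25% away from the need. Roughly a quarter would give a trial with less than 50% power, and roughly a quarter one more than twice the size needed. The true effect, the ICC, the even split and the next trial's error rates are all assumed. The imprecision persists across d = 0.3 to 0.8 and ICC 0 to 0.05 or 0.10, and is smallest at the largest effect.

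The point says nothing against the hypothesis tests of this trial. That the word promising is left undefined is a wording matter only.

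**What to change.** In Sample Size and Power Considerations, replace the effect-size basis with three statements.

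1. The full-scale trial's target difference will be a minimum important difference on one named outcome, set and recorded by the investigators before any arm comparison is seen. The STAXI-2 trait anger scale, already used for eligibility, is one candidate. The documents give no value and none is proposed here.
2. The pilot will supply only the SD, therapy-group ICC, baseline to post-treatment correlation and retention. The SD is far better estimated than the effect. With 58 degrees of freedom and no clustering, its standard error is about 1/√(2 × 58) = 9% of its value, or about 19% on N. The effect's is 0.258/0.5 = 52% of its value at d = 0.5. The ICC will be imprecise from about ten groups, so N should be shown over a range of ICC values.
3. Arm differences will be reported with intervals at a stated level, used only to check whether they are compatible with the minimum important difference.

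Optionally, define or drop the word promising.

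**Cost.** Rewording in one section and one difference agreed in advance; no extra patients, visits or data. The investigators must justify that difference, and the planned trial may come out larger than an optimistic pilot would suggest.

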- Five Facet Mindfulness Questionnaire (FFMQ; Baer et al., 2008)
- PTSD Checklist for the DSM-V (PCL-5; Weathers et al., 2013)
- Quantity-Frequency Variability Index (QFI; Cahalan, Cisin, & Crossley, 1969)
- Alcohol Dependency Scale (ADS; Skinner & Allen, 1982)

Interim Assessments: During the intervention period, at two time points (weeks 3 and 6 of therapy), participants will be asked to complete the STAXI-2, the BPAG, the FFMQ, the PCL-5, the QFI, and the ADS.

Post-treatment Session: Participants will complete the same battery of self-report questionnaires that was completed at the baseline session. In addition, participants also will complete the following assessments. (See Figure 3 below outlining the order of tasks during experimental portion of the post-treatment session.)

(c) Psychophysiological Assessments: During the experimental portion of the post-treatment session, physiological measurements will be recorded to assess reactivity during exposure to the trauma cue (script). Participants will sit quietly for 5 minutes to collect baseline (B) physiological assessments. This will be followed by the trauma-script reading (TR) and then the trauma-script imagery (TI) segments followed by a resting period (R) and assessment of subjective experiences.

Physiological measurements will include skin conductance levels (SC) and heart rate levels (HR). A BIOPAC MP150 system (BIOPAC, Santa Barbara, CA) that includes modules for HR and SC will be used to record physiologic analog signals. Physiologic analog signals will be digitized by an analog to digital converter. A notebook computer (IBM-compatible) with BIOPAC Acknowledge© software will be used to sample and store the digitized physiologic signals. Interbeat interval will be recorded in milliseconds via standard limb electrocardiogram leads connected to a High Gain Bioamplifier and converted to HR. Skin Conductance (SC) will be measured by an Isolated Skin Conductance coupler using a constant .5 V through 2, 9-mm (sensor diameter) Ag/AgCl electrodes filled with electroconductive gel placed on the hypothenar surface of the subject's non-dominant hand in accordance with published guidelines. The SC electrodes will be separated by 14 mm, as determined by the width of the adhesive collar.

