Primary Aim 1 Hypothesis 1.1: Participants assigned to MBSR will report decreased levels of self-reported anger and aggression at post-treatment and at the 3-month follow up compared to those assigned to the TREC group. Scores on the State Trait Anger Expression Inventory-2 and the Buss-Perry Aggression Questionnaire will be used as the primary outcome variables for self-report anger and aggression. Intent-to-treat analyses will be conducted for these outcomes, which will be examined separately. Bonferroni adjustments will be implemented to control for Type 1 error. These data will be analyzed using mixed effects models with treatment, time, and treatment x time interaction as fixed effects. Subject will be the clustering factor and it will be nested within therapy group which will also be considered random. Different variance-covariance structures will be considered and the best one selected based on Schwartz’ Bayesian Information Criterion (BIC). Mixed effects models are the preferred method for analyses of such data as they use all available data on an individual, give unbiased results under general missing data assumptions and provide flexibility in modeling the correlation structure within subject. Significant interactions will be examined further using post-hoc tests.

Primary Aim 1, Hypothesis 1.2: Participants assigned to MBSR will exhibit lower levels of anger and aggression on the TRT compared to those assigned to the TREC group. Mixed effects models will be used to compare the TREC group to the MBSR group on responses on the TRT: (1) mean shock level across the TRT, and (2) total number of “20” shocks chosen on the TRT following the same strategy as for primary aim 1 hypothesis 1.1.

Secondary Aim 1, Hypothesis 1.1: Those assigned to MBSR will exhibit significant decreases in HR and SCL and increases in emotion regulation compared to those assigned to the TREC group. Mixed effects models will be used to compare the TREC group to the MBSR group on physiological variables (HR, SCL) and emotion regulation (DERS-S) following the same strategy as for primary aim 1, hypothesis 1.1.

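### For STAXI-2 and BPAQ, the effect size that will plan the next RCT comes from a t-test on veterans with a post-treatment score, not from the intent-to-treat mixed model already planned for the same outcomes

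*Combined protocol and SAP*

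**What the plan says.** Two parts of the plan treat the same outcomes differently.

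- **Sample Size and Power Considerations.** The pilot's main job is described as informing a later full-scale trial. For the self-report measures: "Effect sizes for determining the sample size for the larger RCT will be calculated based on differences between the baseline and post-treatment scores". Then: "Comparisons will be made using a two-sample t-test". The section adds confidence intervals around the observed effect and consultation with clinicians, and goes on to discuss clustering by therapy group. It gives no rule for a missing post-treatment score and no attrition rate.
- **Data Analyses, Primary Aim 1 Hypothesis 1.1** (STAXI-2 and BPAQ). "Intent-to-treat analyses will be conducted for these outcomes, which will be examined separately". The model: "These data will be analyzed using mixed effects models with treatment, time, and treatment x time interaction as fixed effects". Part of the reason given for mixed models is that "they use all available data on an individual, give unbiased results under general missing data assumptions".

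The data behind each come from the assessment sections. Under Interim Assessments: "During the intervention period, at two time points (weeks 3 and 6 of therapy), participants will be asked to complete the STAXI-2"; the BPAQ is collected at the same visits (Table 1). Under Post-treatment Session: "After all participants have completed their assigned interventions (TREC or MBSR) they will be scheduled for the post-treatment session". The opening paragraph of Data Analyses provides for visual inspection for missing values but names no method for handling them.

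**The concern.** A baseline-to-post difference exists only for someone with both scores. The t-test therefore compares those assessed at post-treatment. A veteran who gave scores at baseline, week 3 and week 6 and then left contributes nothing to the planning effect, although the mixed model would use those scores.

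This matters when the reasons for leaving differ between arms. If veterans who are not improving leave one arm more than the other, the difference among those who remain is not the difference among those randomised. The later trial would be sized on it, and the pilot would carry two effects for one contrast, based on different sets of people.

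Different dropout in the two arms is plausible, though not shown: MBSR sessions last two hours and TREC sessions one hour.

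**Working it through.** **Nothing to reproduce.** The pilot's 60 is not derived from an effect size, alpha or power, and no RCT sample size is stated. The figures below illustrate how far the two estimates can part.

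**Assumed inputs** (none is in the documents):
- visits at baseline, week 3, week 6 and post-treatment; SD 1 at each; correlation 0.6 between any two
- MBSR benefit over TREC of 0, 0.2, 0.35 and 0.5 SD at those visits
- dropout after week 3 or week 6, logistic in the last observed change; log-odds slopes of 1 to 1.5 per SD of change give values of the size shown
- about 25% missing at post-treatment in each arm
- RCT at two-sided 0.05 and 80% power; therapy-group clustering left out

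**Step 1, scale.** SD of change = √(2(1 − 0.6)) = 0.894. A true difference of 0.50 is 0.50/0.894 = 0.56 SD of change.

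**Step 2, large-sample results.**

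| Dropout process | Difference among those assessed | Maximum likelihood, all available scores |
|---|---|---|
| Same in both arms | 0.50 | 0.50 |
| Related to change in MBSR only | about 0.62 | 0.50 |
| Related to change in TREC only | about 0.39 | 0.50 |
| MBSR only, depending on the unseen post-treatment score | 0.73 | 0.66 |

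The last row matters: using all available data removes the bias only when dropout depends on scores that were seen.

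**Step 3, what this does to the RCT.** Per arm, n ≈ 2(1.960 + 0.842)²/d² = 15.70/d², with d in SDs of change; the noncentral t adds one or two.
- True effect: d = 0.559; 15.70/0.3125 = 50.2; noncentral t gives 52.
- Difference 0.62: d = 0.62/0.894 = 0.693; 15.70/0.481 = 32.7; noncentral t gives 34. Power at the true 0.559 is then about 62%.
- Difference 0.39: d = 0.39/0.894 = 0.436; 15.70/0.190 = 82.6; noncentral t gives 84. Power at the true 0.559 is then about 95%, so the trial is larger than needed.

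**Step 4, a second set-up.** Effects in SDs of change, true value about 0.50, dropout after week 6 only. Dropout unrelated to outcome (20%) gave 0.50. Poor responders leaving MBSR only (26–30% missing in MBSR, 20% in TREC) gave 0.60–0.66. Poor responders leaving TREC only gave 0.40. One rule in both arms, with 21% missing in MBSR and 26% in TREC, gave 0.48. The estimate using interim scores stayed at 0.50–0.51 throughout.

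**Step 5, does the confidence interval cover this?** At d = 0.5 with 30 per arm (equal arms assumed), SE = √(2/30 + 0.25/120) = 0.262, so the interval is −0.01 to 1.01. It reflects sampling error and is centred on whatever the assessed set gives.

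**The case against.** **Sampling error is larger than the bias.** On these assumptions the SE of the change difference at 30 per arm is 0.894 × √(2/30) = 0.23, against biases of about 0.11 to 0.12 in the first three rows of the table. The plan already warns that pilot effect sizes may be inaccurate. This stands, and it keeps the point in proportion. It is no reason to keep the more exposed estimate when the other is already planned.

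**The mixed model is no cure.** It was unbiased here because dropout was made to depend on observed scores; otherwise it too is off (0.66). This also stands, and is why missing numbers by arm should be reported.

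**The plan may intend imputation.** It does not forbid it, but it names no method, and a t-test on differences as written needs both scores.

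**The RCT is not yet written.** True: its attrition allowance and analysis set can be fixed in its own protocol. The effect size it inherits is fixed here.

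A reader might infer three stronger things that the documents do not support:
- *That the t-test set is treatment completers.* The Post-treatment Session sentence gives timing. The Overview has all participants attending, a positive urine screen leads to rescheduling under Drug and Alcohol Screening, and nothing bars a veteran who stopped therapy from attending. The set is those assessed.
- *That the RCT will be underpowered.* That follows only if dropout tilts one way. The mirror case oversizes it, and nothing in the documents favours either.
- *That every planning effect size is affected in a way the model could mend.* For heart rate, skin conductance and the DERS-S the plan uses difference scores, ending with "emotion regulation obtained during the experimental portion of the post-treatment session". These exist only at that session, so a mixed model would rest on attendees too.

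**Conclusion.** The point holds for STAXI-2 and BPAQ. The planning effect is computed on veterans with a post-treatment score and sets aside interim data that the plan's own intent-to-treat model would use. The confidence interval, clinician consultation and clustering discussion do not address who is missing.

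The size cannot be derived from the documents. Under the stated assumptions (true difference 0.50 SD, about 25% missing per arm) the assessed-only difference ranges from about 0.39 to about 0.62, or 84 down to 34 per arm against 52. There is no bias when dropout is alike in both arms or unrelated to outcome. The case for change is that the all-available-data estimate is less prone to bias and nearly free, not that a particular loss of power is expected.

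**What to change.** In Sample Size and Power Considerations, for STAXI-2 and BPAQ only, replace the t-test on differences with wording such as:

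> The planning effect is the MBSR-TREC contrast in change from baseline to post-treatment from the Hypothesis 1.1 mixed model, fitted to all randomised participants with all available visits (including weeks 3 and 6), with its confidence interval, divided by a stated SD that matches the planned RCT analysis. The difference among those with a post-treatment score, and the number missing by arm, are reported beside it.

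The SD must be named because it changes the answer: a difference of 0.5 needs 64 per arm if divided by an SD of 1 for the post-treatment score, and 52 if divided by the 0.894 SD of change.

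A value assuming that dropouts gain nothing may be shown as a sensitivity bound. With 20% dropout, 0.5 × 0.8 = 0.4, which needs 100 per arm rather than 64. It must not then be divided by (1 − attrition): 100/0.8 = 125 would count dropouts once as measured without gain and again as missing.

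The cost is SAP wording; the model and visits are already planned. The downsides are that the planning effect may turn out smaller, and that the model removes bias only when dropout depends on observed scores. Heart rate, skin conductance and DERS-S stay outside this change.
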